Aim 1 (Phase 1): Estimate the differential brain fMRI response between XRNTX and XRBUP in OUD treatment groups. We hypothesize that (**H1**) XRBUP and XRNTX will modulate the regional brain activity in the two-key cognitive-behavioral domains and measures of brain connectivity from pre-treatment (PRE) to on-treatment (ON) and this response will differ between the two medications. Milestone for transition to Phase 2: The MAT group (XRNTX, XRBUP) by Session (PRE, ON) **interaction** will have at least small ($d' \geq 0.2$) effect size in all brain measures.

H1a: Incentive salience (opioid cue-reactivity task): The decrease in the brain response to drug related stimuli (ON minus PRE) in the medial prefrontal cortex (mPFC) and the ventral striatum (VS) will be **greater** in the XRNTX than in the XRBUP group.

H1b: Executive function (Go-NoGo task): XRNTX will improve the efficiency of response inhibition more than XRBUP, leading to a greater **decrease** in the brain signal (ON vs PRE) during the NoGo trials in the inferior frontal cortex in the XRNTX group (see A.2.b).

H1c: Resting state functional connectivity (rsFC): change (ON vs PRE) in the rsFC between the VS and the right inferior frontal gyrus (rtIFG) and the mPFC will be **greater** in the XRNTX (vs. XRBUP group).

Aim 2 (Phase 2): Confirm in the full sample (n=200), the significance of MAT (XRNTX, XRBUP) by Session (PRE, ON) interaction in all domains from Aim 1. Test the explanatory value of integrated brain-behavior models of relapse vulnerability, identify differences in variable loading between MAT group, and explore potential mechanism of individual variability in treatment outcome.

H2a: Using logistic regression, we will test the explanatory value of brain signal in modeling treatment failure (Section **C.5.c**) and identify specific variables that differentiate MAT groups (interaction).

H2b (Exploratory): Test if the models that include brain response better explain treatment success or failure when compared to those fitted solely with demographic and clinical measures: demographic + clinical measures vs. demographic + clinical measures + brain response).

3.3 Secondary Study Endpoints (abbreviations spelled out on Page 27, “STUDY MEASURES”):

Depression (HAM-D2); Anxiety (HAM-A); Opioid Withdrawal (COWS); Opioid Craving (Opioid Craving Scale); TLFB interview; Percent UDS positive for cocaine (Ten-drug urine screen)

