9 STATISTICAL CONSIDERATIONS

9.1 Statistical Hypotheses

Overview of primary hypotheses: Our primary response will be a binary indicator of treatment failure on the XRNTX or XRBUP regimen, defined as ≥ 2 weekly UDS positive for opioids, or self-report of ≥ 2 periods of three or more days of opioid use, or refusing XRNTX or XRBUP, or dropping out of study entirely. In hypotheses H1a and H1b, we are examining the effects of small, pre-specified, sets of measures, so our analyses will focus on model fit and prediction, and not on model selection. In hypothesis H1c, we search for best sets of predictors among demographic and clinical-behavioral variables, and over sets of brain/neural measures, so our focus is on model selection and on avoiding overfitting to the available data.

R61 Phase:

Hypothesis H1 (fMRI): For each of the cue reactivity (H1a), response inhibition (H1b), and connectivity (H1c) brain measured, we have a small number of neural responses associated with one or two regions of interest. These variables are continuously distributed, so we will test Hypotheses 1a, 1b and 1c using a repeated measures analysis of variance (rm-anova). The models will include a within-subject factor for Session (PRE vs ON) and a between-subject factor Group (XRNTX vs XRBUP), and their interaction. To accommodate the anticipated non-normal distributions of the response, we will use a generalized estimating equation (GEE) approach, using robust standard errors, using a compound symmetry working correlation structure for the within-subject correlations between the PRE and ON fMRI scans (Diggle PJ et al 2002). We will perform the rm-anova separately for each ROI (mPFC and VS for H1a, IFC for H1b, and VS-rtIFG and VS-mPFC for H1c). The hypotheses will be addressed by the Session by Group interaction, and we will obtain estimates and standard errors of the PRE vs ON change within each of the two groups, along with the size, standard error and significance of the differences between these estimates.

Sample size considerations for sample: The sample size is adequate for application of the GEE methods to obtain robust standard error (Lipsitz et al 1994). For a test of the PRE vs ON effect, our sample yields 80% power for a one-sided test that the ON levels will be Cohen's $d=0.4$ lower than the PRE levels, consistent with a decrease of Cohen's $d=0.5$ observed in our preliminary data and a decrease of Cohen's $d=0.3$ in the Suboxone sample.

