Effects of neural response on relapse vulnerability: Our primary outcome combines adherence to treatment and frequency of illicit opioid use during treatment. The primary outcome is a binary indicator of treatment success: if a patient provides ≥ 2 weekly UDS positive for opioids, or self-report of \geq two or more periods of ≥ 3 days of opioid use, or refuses XRNTX or XRBUP, or drops out of treatment entirely, then they will be classified as a treatment failure; otherwise they will be classified as a treatment success. We will calculate the PRE-ON change in %-signal-change for each of the regions and neural responses described in the R61 phase. We will use logistic regression models to predict the log-odds of treatment success (Aitkin et al 2009). The predictors in the model will be a binary factor for Group (XRNTX vs. XRBUP), and the neural change scores. We anticipate that there will be some greater PRE to ON changes in the XRNTX group than in the XRBUP group, so there will be some confounding between the effects of change score and the effects of Group on the rates of positive UDS. Thus, we will include Group first in our model, so evaluating the Group effect separate from the change-score effects, and then include the change scores in a model including Group, so evaluating the additional effect of change-scores in addition to the existing effects of Group. To assess whether the effects of the change scores differ between the XRNTX and XRBUP groups, we will also test for interaction effects between Group and each of the change-scores, by adding the interaction terms to the model that includes the group and neural change score main effects. We will check the assumptions underlying the logistic regression models (e.g. linearity of covariates effects on log-odds, outliers, influential observations) using standardized residuals, influence diagnostics, and graphical displays.

Sample size considerations for the sample: Analyses of Session by Group effects on neural response: For a one-sided test that the PRE vs ON effect is larger in the XRNTX group than in the XRBUP group, our sample of 70 per group yields 81% power for an effect of $d=0.42$ or greater. This effect is similar to the effects observed in the preliminary data. On the basis of the preliminary data we anticipate Group by Session effects of approximately $d=0.38$ in the VS and $d=0.42$ in the mOFC.

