Analyses of effects of neural response on relapse vulnerability: We consider the effect for an individual neural change variable, in a model where Group is included, assuming a small effect for Group (odds ratio = 1.25). We have three domains, with two neural variables in two domains and one in the other, so we provide power for $\alpha=0.05$ and for $\alpha=0.025$. For $\alpha=0.05$ we have 80% power for an odds ratio of 1.75 or higher per standard deviation increase in a neural variable; for $\alpha=0.025$, we have 80% for an odds ratio of 1.86 or higher.

Analyses of polysubstance use outcomes: We will also examine the effects of Group and neural change variables on other substance use outcomes, including self-report and UDS measures of opioid, stimulant, and benzodiazepine use. Here, we will use the self-report and UDS measures to create binary weekly measures of use for each substance, and use GEE repeated measures logistic regression models, with Group and the neural change measures as predictors, to estimate and test effects. These secondary analyses will be subject to missing data. We anticipate 25% dropout rates. To assess possible effects of nonignorable missingness on inference, we will perform sensitivity analyses using pattern-mixture models and selection models. For pattern mixture models, subjects are grouped on the basis of their pattern of missing data, and the resulting categorical factor is included in the analyses as a main effect and interaction with predictors of interest. Overall predictor effects may be found by averaging over the patterns (Molenberghs et al 2005). Selection models (Molenberghs et al 2005) take a different approach, by explicitly modeling the probability of drop out, and incorporating the predicted probabilities into the main longitudinal analysis, with the dropout and response processes included in a single bivariate model. Comparisons between the predictions of the primary analyses, and each set of pattern mixture and selection models, provides some evidence for assessing the sensitivity of results to missing data.

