
9.2 Sample Size Determination:

Analyses of Session by Group effects on neural response: For a one-sided test that the PRE vs ON effect is larger in the XRNTX group than in the XRBUP group, our sample of 80 per group yields 81% power for an effect of $d=0.42$ or greater. This effect is similar to the effects observed in the preliminary data. On the basis of the preliminary analysis, we anticipate Group by Session effects of approximately $d=0.38$ in the VS and $d=0.42$ in the mOFC.

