Primary Hypothesis: Estimate the differential brain fMRI response between XRNTX and XRBUP in OUD treatment groups. We hypothesize that **(H1)** XRBUP and XRNTX will modulate

the regional brain activity in the two-key cognitive-behavioral domains and measures of brain connectivity from pre-treatment (PRE) to on-treatment (ON) and this response will differ between the two medications. Milestone for transition to Phase 2: The MAT group (XRNTX, XRBUP) by Session (PRE, ON) **interaction** will have at least small ($d' \geq 0.2$) effect size in all brain measures.

H1a: Incentive salience (opioid cue-reactivity task): The decrease in the brain response to drug related stimuli (ON minus PRE) in the medial prefrontal cortex (mPFC) and the ventral striatum (VS) will be **greater** in the XRNTX than in the XRBUP group.

H1b: Executive function (Go-NoGo task): XRNTX will improve the efficiency of response inhibition more than XRBUP, leading to a greater **decrease** in the brain signal (ON vs PRE) during the NoGo trials in the inferior frontal cortex in the XRNTX group.

H1c: Resting state functional connectivity (rsFC): change (ON vs PRE) in the rsFC between the VS and the right inferior frontal gyrus (rlIFG) and the mPFC will be **greater** in the XRNTX (vs. XRBUP group).

Secondary Hypotheses: Confirm in the full sample (n=140), the significance of MAT (XRNTX, BUP-NTX) by Session (PRE, ON) interaction in all domains from Aim 1. Test the explanatory value of integrated brain-behavior models of relapse vulnerability, identify differences in variable loading between MAT group, and explore potential mechanism of individual variability in treatment outcome.

H2a: Using logistic regression, we will test the explanatory value of brain signal in modeling treatment failure and identify specific variables that differentiate MAT groups (interaction).

H2b (Exploratory): Test if the models that include brain response better explain treatment success or failure when compared to those fitted solely with demographic and clinical measures: demographic + clinical measures vs. demographic + clinical measures + brain response).

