10.2 LIMITATIONS

LIMITATIONS AND ALTERNATIVE RESULTS: We have carefully considered **potential limitations of our study and alternate designs**. Several domains that may be of interest are not included (e.g., Affect Regulation) because task selection is based on a conceptual model and to optimize subject burden. In our past experience, scanning participants for > 1-hour results in substantial movement artifact that can bias imaging results. Regarding affect regulation, we are including a well-validated self-report measure and other psychological measures as baseline predictors/covariates in the analysis. We have focused on a model-driven analysis. However, this sample may allow a data-driven, model-free approach. This limitation can be addressed by exploratory analyses using advanced methods (e.g. machine learning). Although our proposed sample size provides ample power to test our primary hypotheses and model building, validation will likely require an independent sample rather than resampling techniques for cross validation.

Strengths of Proposed Research: To our knowledge, this would be the first investigation of the use of = BOLD fMRI signal during cognitive tasks and connectivity to characterize treatment outcomes for two extended release MAT medications. The study is carefully designed and powered to evaluate the outcomes of interest. The use of larger sample sizes than previous research and novel medication will provide the strongest possible test of our hypotheses. We have demonstrated the feasibility of recruitment to studies with similar requirements, have identified brain regions of interest through our prior research, and have performed extensive pilot-testing of all paradigms. The significance of this project is its potential to advance theory and treatment by elucidating brain-behavior mechanisms.

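### The 81% power is for a single ROI test, whereas Aim 2 seeks a significant interaction in all three domains; the plan gives neither a success rule nor the power for that aim

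*Combined protocol and SAP*

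**What the plan says.** Section 9.2 supports the sample with a single statement: "our sample of 80 per group yields 81% power for an effect of $d=0.42$ or greater". Section 9.1 prints the same power and effect for a smaller group: "our sample of 70 per group yields 81% power for an effect of $d=0.42$ or greater". Both are introduced in the same way: "For a one-sided test that the PRE vs ON effect is larger in the XRNTX group than in the XRBUP group". Both sections anticipate d of about 0.38 in the VS and 0.42 in the mOFC. No effect size is given for the inferior frontal cortex or for the two connectivity measures.

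Aim 2, in Section 3.2, is to confirm "the significance of MAT (XRNTX, XRBUP) by Session (PRE, ON) interaction in all domains from Aim 1". Section 9.4.1 repeats it: "Confirm in the full sample (n=140), the significance of MAT (XRNTX, BUP-NTX) by Session (PRE, ON) interaction in all domains from Aim 1". The analysis in Section 9.1 is by region: "We will perform the rm-anova separately for each ROI (mPFC and VS for H1a, IFC for H1b, and VS-rtIFG and VS-mPFC for H1c"). That section then refers to five hypotheses and reruns the same models unchanged in Phase 2. In its relapse-model power paragraph it counts three domains.

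Section 10.2 concludes that "our proposed sample size provides ample power to test our primary hypotheses and model building".

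For the Phase 2 interaction tests the plan gives no success rule, alpha, correlation between ROIs or multiplicity rule. The only alpha levels printed belong to the logistic relapse models: "so we provide power for $\alpha=0.05$ and for $\alpha=0.025".

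**The concern.** The power figure and the aim describe different events. One test reaching significance is a single event. A significant interaction in every domain requires several tests to succeed together, and the chance of that is usually lower than the chance for any one of them.

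Two things are at stake. A reader who sees 81% beside Aim 2 will take it as the chance of achieving Aim 2 if the drugs differ as planned. And if one region or domain then misses significance, that reader may conclude that the drugs do not differ there, although such a miss would be common even with every planned effect present.

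**Working it through.** **Inputs from the plan.** n = 70 per group (9.1) or 80 per group (9.2); one-sided test; d = 0.42 for the powered effect; d = 0.38 in the VS; five ROI tests in three domains (2, 1 and 2 ROIs).

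**Assumptions, not in the plan.** One-sided alpha 0.05 per test; d = 0.42 in every ROI, with the mOFC value standing in for the mPFC named in H1a; one common correlation r between the test statistics, varied from 0 to 0.7.

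**Step 1: the plan's own figure.** With d as the standardised difference in PRE-to-ON change, power = Φ(d·√(n/2) − 1.645).

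- 70 per group: 0.42 × √35 = 2.485; 2.485 − 1.645 = 0.840; power 80.0% (noncentral t: 79.6%).
- 80 per group: 0.42 × √40 = 2.656; 2.656 − 1.645 = 1.011; power 84.4% (noncentral t: 84.1%).
- 80 per group at one-sided 0.025: 2.656 − 1.960 = 0.696; power 75.7%.

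The printed 81% is therefore approximately a single-test figure at one-sided 0.05 with 70 per group. It does not reproduce at 80 per group.

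**Step 2: power for Aim 2 under three possible rules.** Let p be single-test power. With independent tests:

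- All five ROIs: p⁵. 0.7995⁵ = 0.327; 0.8441⁵ = 0.429.
- One test per domain: p³. 0.7995³ = 0.511; 0.8441³ = 0.601.
- At least one significant ROI in each domain: p·[1 − (1 − p)²]². At 70 per group, 0.7995 × 0.9598² = 0.737. At 80 per group, 0.8441 × 0.9757² = 0.804.

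For r > 0, condition on a shared standard normal factor u. Each test's success probability becomes Φ((d·√(n/2) − 1.645 + √r·u)/√(1 − r)). Put that in place of p in the formulas above and integrate over u. Ranges over r = 0 to 0.7:

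| Rule for confirming all domains | 70 per group | 80 per group |
|---|---|---|
| All five ROIs significant | 33–59% | 43–66% |
| One test per domain (three tests) | 51–66% | 60–72% |
| At least one significant ROI in each domain | 73–75% | 79–80% |

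Even at r = 0.9, the five-ROI rule gives only 69% and 75%.

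**Step 3: the plan's own VS effect.** At d = 0.38:

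- 70 per group: 0.38 × √35 = 2.248; 2.248 − 1.645 = 0.603; power 72.7%.
- 80 per group: 0.38 × √40 = 2.403; 2.403 − 1.645 = 0.758; power 77.6%.

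Joint power cannot exceed the power of any required component. A rule that requires the VS test is therefore capped at 73% or 78%, whatever r is. With 0.38 in the VS and 0.42 elsewhere, the five-ROI rule gives 30–56% (70 per group) and 39–63% (80 per group).

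**Step 4: how often something misses when every effect is d = 0.42.** These are complements of the table. At least one of five ROIs misses in 34–57% of trials at 80 per group (41–67% at 70). With one test per domain, at least one domain misses in 28–40% (34–49% at 70).

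**The case against.** The best defence is that the plan never writes an all-must-succeed rule. Section 9.1 fits each ROI model separately and promises estimates, standard errors and significance for each. Quoting power per test is ordinary practice for hypotheses stated one by one. Section 3.1 also allows some Phase 1 probes to be dropped, so five Phase 2 tests are not guaranteed. And if one significant ROI is enough to confirm a domain, power at 80 per group is 79–80%, within about 2 points of the printed figure.

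Much of this stands, and it rules out two stronger readings. A reader might infer that the trial's confirmatory power is 33–66%. The plan does not support that: it speaks of domains, not of all five ROIs, and the range joins the low end at 70 per group to the high end at 80 per group. A reader might also infer that a third to two thirds of trials would miss a domain. That is the miss rate for any one of five ROIs; the rate for domains is lower, as Step 4 shows.

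The defence does not remove the gap. The aim is written as significance in all domains. H1a and H1c each name their two measures jointly, which sits poorly with a one-ROI-is-enough rule. For the Phase 1 milestone, Section 9.1 does write a partial rule (two of three domains), whereas Aim 2 has none. The lenient rule is not stated anywhere, and at 70 per group it still gives only 73–75%.

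**Conclusion.** The concern holds in this form: the 81% is single-ROI power at d = 0.42, it is not the power for Aim 2, and the plan supplies neither the rule nor the figure for that aim. Depending on the rule intended, power lies between 43% and 80% at 80 per group, or between 33% and 75% at 70 per group.

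Those figures rest on an assumed one-sided alpha of 0.05, an assumed correlation of 0 to 0.7, and d = 0.42 carried over to ROIs for which the plan gives no effect size. A stricter alpha lowers them: at one-sided 0.025 the five-ROI rule gives 25–53% at 80 per group. The VS cap of 73% or 78% needs no assumption about correlation, only the alpha and the plan's own d = 0.38.

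The claim of ample power in Section 10.2 is not supported for the all-domains aim under most of these rules.

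**What to change.** - In 9.1 and 9.2, label the 81% as the power of a single ROI interaction test at d = 0.42, and state its alpha.
- State which rule Aim 2 means: all five ROIs, one named test per domain, at least one ROI per domain, or another rule.
- Beside the 81%, print the power under that rule, with the alpha, the correlation range and d = 0.38 for the VS. Use one analysable n throughout. The plan now has 70 and 80 per group, and full samples of 140 (9.1, 9.4.1), 160 (5.3) and 200 (Aim 2 in 3.2).
- In 10.2, limit the claim of ample power to single-ROI tests.
- State that a non-significant ROI or domain is not evidence that the drugs do not differ there.

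Rewording Aim 2 as separate claims for each domain is possible, but it loosens the criterion and statisticians could differ on it. If it is done, the plan must say how multiplicity is handled. Five independent tests at one-sided 0.05 have a 1 − 0.95⁵ = 22.6% chance of at least one false positive. A rule that accepts either of two ROIs in a domain raises the same issue.

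The cost is some wording and one short calculation, plus a less favourable printed figure for the aim. No change in enrolment is needed.

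### The stated 81% power is at d=0.42, cited for a region (mOFC) not named in the models; at the d=0.38 cited for the tested VS it is about 72% or 77%

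*Combined protocol and SAP*

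**What the plan says.** The Phase 2 power text in Section 9.1 concerns a directional comparison: "For a one-sided test that the PRE vs ON effect is larger in the XRNTX group than in the XRBUP group". It claims that "our sample of 70 per group yields 81% power for an effect of $d=0.42$ or greater". Section 9.2 repeats the statement with a larger sample: "our sample of 80 per group yields 81% power for an effect of $d=0.42$ or greater". Both sections describe 0.42 as in line with the preliminary data, and both name the same two anticipated interactions: "we anticipate Group by Session effects of approximately $d=0.38$ in the VS and $d=0.42$ in the mOFC".

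The regions to be modelled are listed in Section 9.1 under Hypothesis H1: "mPFC and VS for H1a, IFC for H1b, and VS-rtIFG and VS-mPFC for H1c". The hypotheses in Sections 3.2 and 9.4.1 likewise name the mPFC. The mOFC appears only in the power text and in a preliminary-figure caption in Section 4.2.

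The Phase 1 power text in Section 9.1 cites within-group changes in support of a PRE versus ON test. It is "consistent with a decrease of Cohen's $d=0.5$ observed in our preliminary data", and it adds a decrease of d=0.3 in a Suboxone sample. No region or SD unit is given for either figure, and no drug for the 0.5.

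**The concern.** A power statement should refer to the tests that will be run. Here the only effect size at which power is quoted belongs, by name, to a region outside the model list. The one cited effect that does belong to a listed region is smaller and has no power figure. Section 10.2 nevertheless describes the sample as amply powered for the primary hypotheses. A reader faced with a null VS result would take the test to have been more sensitive than the plan's own anticipated effect implies.

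Two things make the figure harder to rely on. One power value is paired with two sample sizes. And the preliminary effects are given without the details needed to relate them to each other or to the planned tests.

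**Working it through.** **Inputs**
- Sidedness: one-sided (Sections 9.1 and 9.2).
- Sample: 70 per group (Section 9.1, total 140) or 80 per group (Section 9.2; Section 5.3 gives a total of 160).
- Anticipated interactions: 0.42 (mOFC) and 0.38 (VS).
- Alpha: not stated for this test. I assume one-sided 5% and also show one-sided 2.5%. The 0.05 and 0.025 in Section 9.1 belong to the logistic-regression power.
- Scale: d is taken as the difference in mean PRE-to-ON change divided by a common SD of change, with equal groups and both scans available. With two sessions and complete pairs, the Session by Group term is the difference in mean change, so a two-sample comparison of change scores applies.

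**Formula.** Power ≈ Φ(d√(n/2) − z), with z = 1.645 at one-sided 5%. The exact version uses the noncentral t with 2n − 2 degrees of freedom and noncentrality d√(n/2).

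**Step 1: the plan's own figure (d=0.42, one-sided 5%)**
- 70 per group: 0.42 × √35 = 2.485; 2.485 − 1.645 = 0.840; Φ = 80.0% (noncentral t 79.6%).
- 80 per group: 0.42 × √40 = 2.656; 2.656 − 1.645 = 1.011; Φ = 84.4% (noncentral t 84.1%).

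So 81% is matched to within about a point at 70 per group but not at 80. With 80 per group, 81% power is reached at d = (1.645 + 0.878)/√40 = 0.40. A sample of 72 per group (80 less 10%) would give 80.9% by the normal formula, but Section 9.2 does not say that such a loss was applied.

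**Step 2: the VS effect (d=0.38, one-sided 5%)**
- 70 per group: 0.38 × √35 = 2.248; 2.248 − 1.645 = 0.603; Φ = 72.7%.
- 80 per group: 0.38 × √40 = 2.403; 2.403 − 1.645 = 0.758; Φ = 77.6%.

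Noncentral t results:

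| d | n per group | one-sided 5% | one-sided 2.5% |
|---|---|---|---|
| 0.42 | 70 | 79.6% | 69.4% |
| 0.42 | 80 | 84.1% | 75.2% |
| 0.38 | 70 | 72.3% | 60.7% |
| 0.38 | 80 | 77.3% | 66.6% |

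**Step 3: sample for 81% at d=0.38.** At one-sided 5%, n = 2(1.645 + 0.878)²/0.38² is just over 88, so 89 per group, more than either stated sample.

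**Step 4: the other tested measures.** No preliminary interaction effect is cited for the IFC, VS-rtIFG or VS-mPFC, nor for the mPFC under that name. Power for these cannot be recomputed from the documents, and carrying the VS value over to them would have no support.

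**The case against.** The plan never says that the VS test has 81% power. It makes a detectable-effect statement, for 0.42 or more, and then openly lists 0.38 for the VS. That is correct, and nothing in the sentence is false. But it serves as the sample-size justification, and it leaves the reader to work out what the tested region gets.

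The mOFC may simply be the sponsor's label for the medial prefrontal region; Section 8 allows in-house templates for defining regions. If so, 0.42 would belong to a tested region, and the VS would no longer be the only one with a cited effect. The text does not say this, and the VS figures would not change.

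At 80 per group the gap is small: 77.3% against 81%, under 4 points. It would also be wrong to say that 81% holds only at the largest cited effect, since at that sample it is reached at 0.40.

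A reader might go further and infer a contradiction: within-group changes of 0.5 and 0.3 differ by 0.2, about half the anticipated interaction, so the trial would be badly underpowered. The documents do not support that. The subtraction gives the interaction only if the 0.5 is the XRNTX effect, both figures come from the same region as the 0.38 or 0.42, they share an SD unit, and the change SDs are equal in the two groups. None of this is stated, and the two figures are offered for a different test. The figure that might identify the samples is not shown in the text available, and its caption is cut off, which is no fault of the plan.

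Nor can the SD unit be recovered from the Phase 1 statement of 80% power at d=0.4. In change-SD units that fits 40 pairs, a number the plan does not give; the 60 planned for Phase 1 would give 92%.

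**Conclusion.** The point holds for the power statement. At the plan's own VS effect, power falls short of 81% by 8.7 points at 70 per group (81 − 72.3) or 3.7 points at 80 per group (81 − 77.3). This rests on an assumed one-sided 5% level and on d being in change-score SD units with equal groups and complete scan pairs. A stricter level lowers the figures further. The mismatch between mOFC and mPFC, and the use of one power value for two sample sizes, can be seen from the text directly.

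The relation between the within-group effects (0.5 and 0.3) and the interactions (0.38 and 0.42) is unreconciled rather than contradictory: the information needed to compare them is missing. No conclusion about power at an interaction of 0.2 follows. Overall this is a moderate overstatement of sensitivity for one tested region, and it does not show that the design fails.

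**What to change.** In Sections 9.1 and 9.2:
- Settle on one analysed sample per group, state the alpha for the one-sided interaction test, and recompute. At one-sided 5%, d=0.42 gives 79.6% with 70 per group and 84.1% with 80.
- Report power at the VS effect of 0.38 beside the figure at 0.42.
- Use one region, mPFC or mOFC, throughout the hypotheses, models and power text. If they are meant to be the same region, say so.
- For each preliminary d (0.5, 0.3, 0.38, 0.42), state the region, the sample and drug, and the SD unit, so that the within-group and interaction figures can be compared.
- State that no preliminary interaction effect is cited for the IFC or the two connectivity measures, and bring the power claim in Section 10.2 into line.

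The cost is wording and a slightly less favourable stated power. These edits do not in themselves change procedures, visits or recruitment.
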